The intervention group for this study are those who will utilize the smartphone app to complete the home-based portion of physical therapy following TKA. The control group are those who have completed traditional home health physical therapy following TKA. Inclusion criteria for the study consists of participants aged 45 to 64, the participant will have undergone unilateral TKA, and the participant should be discharged directly to home from the hospital. Participant's data from the intervention group will be excluded from the study if they do not engage with the app within 24 hours of discharge from the hospital, if the participant neglects to engage with the app over any 24-hour period during the study, or if the participant is readmitted to the hospital at any point during the home bound portion of their recovery.

Subjective outcomes for the participants in the intervention group will be assessed by the Short MAC and objective outcomes will be assessed by measuring total knee ROM improvement. The intervention participants' self-reported frequency of app usage will be compared to the participants' outcomes to determine the dose-response of the app. The Short MAC has been previously shown to be a reliable, valid, and responsive indicator of qualitative improvement in a patient's functional status post-TKA and total hip arthroplasty (THA) by Whitehouse et al (1). Minimum important change for Short MAC has been found to be 7.9 points for small change, 8.4 points for medium change, and 12.1 points for large change (2). The total knee ROM

improvement in the treatment group will be compared against a control group of patients who have completed traditional home care from a variety of physical therapists following TKA.

The primary hypothesis is that the intervention group will show a statistically equal outcome to the control group, demonstrating the efficacy of a low-cost alternative to traditional home care. The null hypothesis is that the research group will not show a statistically equal outcome to the control group. The first alternative hypothesis is that the intervention group will show a statistically significant improvement over the control group. The second alternative hypothesis is that the control group will show a statistically significant improvement over the intervention group.

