Data for the control group will be taken from approximately 30 individuals aged 45 to 64 that have previously completed traditional home health physical therapy care from a variety of physical therapists following TKA. Data for the intervention group will be taken within 48 hours of being discharged from the hospital from approximately 30 participants who agree to use the smartphone app to complete the home-based physical therapy portion of their recovery from TKA. Intervention group participants will complete an introductory meeting with the physical therapist in-person to onboard the patient to the app and perform the initial data collection. Participants in the intervention group will be encouraged to engage with the app 3 to 5 times per day as able. The intervention participant will have the ability to communicate any questions or concerns to the Physical Therapist via e-mail or phone call throughout the homebound portion of their recovery. For safety monitoring, a physical therapist will contact the intervention group participant via phone or e-mail every 24 to 48 hours to ensure no adverse events have occurred. A final in-person meeting will occur between the Physical Therapist and the participant at the conclusion of the homebound portion of the participants' recovery for the purpose of final data collection. A two-tailed t-test for two independent groups will be used to compare the means for total ROM improvement between the intervention group and the control group. Data from the Short MAC will be used to describe the overall subjective effect of the intervention on the patient's functional abilities. The relationship between the Participants self-reported frequency of app usage and their combined subjective and objective outcomes will be used to understand the dose-response of the app. Information about dose-response will be integral in establishing guidelines regarding frequency of app usage for optimal results.

Conclusion

Traditional home health care for individuals recovering from unilateral TKA is expensive and provides a higher level of service than most individuals, aged 45 to 64, require. Use of smartphone technology has the potential to drive down costs while maintaining outcomes for this patient population. The proposed randomized controlled trial would determine the efficacy and proper dose-response of a smartphone app to reduce costs and maintain outcomes for the desired patient population compared to traditional home care.

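### App participants' data are removed for late start, any 24-hour gap in use or readmission, with no matching rule for controls, so the range-of-motion comparison is between groups filtered differently after the start

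*Protocol*

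**What the plan says.** The Methods section of the protocol gives baseline criteria for the study: age 45 to 64, and "the participant will have undergone unilateral TKA, and the participant should be discharged directly to home from the hospital". It then adds exclusions for one group only. "Participant's data from the intervention group will be excluded from the study if they do not engage with the app within 24 hours" of leaving hospital, or "if the participant neglects to engage with the app over any 24-hour period during the study, or if the participant is readmitted" to hospital at any time while home-bound.

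Controls are defined differently: "The control group are those who have completed traditional home health physical therapy following TKA". Their data come from "approximately 30 individuals aged 45 to 64 that have previously completed traditional home health physical therapy care". No late-start, missed-visit or readmission rule is stated for them.

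App participants are "encouraged to engage with the app 3 to 5 times per day as able". On the final measurement: "A final in-person meeting will occur between the Physical Therapist and the participant at the conclusion of the homebound portion" of recovery. On the analysis: "A two-tailed t-test for two independent groups will be used to compare the means for total ROM improvement" between the two groups. No analysis of all enrolled participants is stated. The Objectives section adds a dose-response aim, relating self-reported frequency of app use to outcome.

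**The concern.** Not using the app and being readmitted are two ways in which unsupervised app-based therapy can fail. Removing the people to whom this happens removes part of what the primary objective asks about. The Conclusion says the trial will show whether the app maintains outcomes in the intended patient population. With these exclusions the result describes only those who used the app without a gap and stayed out of hospital.

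The rule takes data out of the study, not out of one labelled analysis, and it defines the only analysis set in the protocol. A later analysis plan would have to contradict the protocol to undo it.

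Three further consequences follow:

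- A participant unable to use the app at all for one day has still followed the as-able instruction, yet is excluded.
- The dose-response analysis is meant to guide recommended frequency of use, but part of its low-use end is removed.
- Readmitted participants drop out of the reported data, although the safety contacts every 24 to 48 hours would still detect the event.

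**Working it through.** **Text check**

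| Filter | App group | Control group |
|---|---|---|
| Baseline criteria | Age, unilateral surgery, discharged home | Same |
| Start within 24 hours | Required | Not stated |
| No 24-hour gap in therapy | Required | Not stated |
| No readmission | Required | Not stated |
| Completed home care | Not stated as such | Required |

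Below the baseline row, no filter applies to both groups. The claim rests on this table. The protocol gives no SD, effect size, margin, alpha, dropout rate or length of the home-bound period, so there is no figure of its own to reproduce. What follows is illustration, and apart from the group size of about 30 every input is assumed.

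**1. Retention in the app group.** Let person i engage on any day with probability p_i = expit(mu + s·z_i), where z_i is standard normal, s is 0.5 to 2, and mu is set so that the mean of p is 0.98 or 0.95. A person is kept for L days with probability p_i^L. Readmission is not modelled.

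- L = 14: retention runs from 0.514 (mean 0.95, s = 0.5) to 0.846 (mean 0.98, s = 2). Of 30 enrolled, 30 × (1 - 0.846) = 4.6 to 30 × (1 - 0.514) = 14.6 are excluded, about 5 to 15.
- L = 7 to 21: retention runs from 0.382 to 0.903.

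**2. Shift in the app mean.** If ROM improvement correlates rho with z, the kept group's mean rises by rho × E[z | kept] SD. With rho 0.3 to 0.5:

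- L = 14: 0.039 to 0.215 SD.
- L = 7 to 21: 0.020 SD (mean 0.98, s = 0.5, L = 7, rho 0.3) to 0.274 SD (mean 0.95, s = 1, L = 21, rho 0.5).

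**3. Shift in the control mean from taking completers only.** If the lowest fraction f on the same trait do not complete, the shift is rho × phi(z_f)/(1 - f), where z_f is the f quantile.

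- f = 0.05: 0.033 SD (rho 0.3) and 0.054 SD (rho 0.5).
- f = 0.20: 0.105 SD (rho 0.3) and 0.175 SD (rho 0.5).

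**4. Net shift, app minus control, L = 7 to 21.**

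- rho = 0.5: from 0.034 - 0.175 = -0.141 SD to 0.274 - 0.054 = about +0.22 SD.
- rho = 0.3: from -0.085 to +0.132 SD.

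Both ranges cross zero.

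**5. Effect on the t-test.** Take a true app deficit of 0.5 SD, 30 controls, two-sided alpha 0.05 (assumed) and L = 14, with 40,000 simulated trials per setting. The table gives the chance of a non-significant result; with no filter it is 52%. The protocol does not say whether its figure of about 30 app participants is before or after exclusions, so both readings are shown.

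| Setting | 30 enrolled | 30 left after exclusions |
|---|---|---|
| App rules, rho = 0 (sample loss only) | 56% to 66% | 52% to 53% |
| App rules, rho 0.3 to 0.5 | 63% to 84% | 58% to 80% |
| Both filters, f = 0.05 | 58% to 79% | 53% to 73% |
| Both filters, f = 0.20 | 40% to 65% | 33% to 55% |

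The rows with both filters are closest to the protocol, because its controls are completers.

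**6. Dose-response.** A correlation of 0.40 between z and outcome falls to between 0.395 and 0.319 among those kept, over 7 to 21 days.

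**The case against.** The best counter-argument is that controls are filtered too. They are known completers, so comparing persistent app users with completers of home care might be a fair contrast of efficacy. The first part stands, and for that reason no net direction is claimed. The second does not follow, because completing home care is not the same condition as having no 24-hour gap and no readmission, and nothing in the protocol makes the two filters equal. A matched comparison of users with completers would be defensible, but the protocol does not set one up.

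Several narrower objections also have force:

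- No rule selects on ROM itself. Readmission is the only clinical outcome selected on, and the calculations leave it out.
- The completer filter is modelled as a hard cut at the bottom of the trait, which gives the largest shift possible for each assumed f and rho. The 0.03 to 0.18 SD range and the -0.14 end of the net range are therefore upper bounds in size.
- The 52% with no filter reflects a different weakness: a non-significant difference in small groups is weak evidence of equality.
- The loss to the dose-response is modest. Under a linear relation, selection on dose weakens the correlation but does not bias the slope. The model also uses a latent tendency to engage, not the self-reported frequency the protocol will analyse.
- The as-able wording qualifies the number of sessions per day, so it conflicts with the rule only for someone who cannot use the app at all for 24 hours.
- The protocol does not say how adverse events will be reported, so it cannot be said that readmissions would go unreported as safety events.

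These points limit the figures and the side arguments. They leave the one-sided rule as it is.

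**Conclusion.** The concern holds, and the rule must be fixed. Followed exactly, the protocol makes its only between-group comparison one of app participants filtered on engagement and readmission against controls filtered on completion. This conclusion comes from the text and needs none of the assumed numbers.

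The size and the net direction are unknown. Under the assumptions above, the net shift could be as large as 0.22 SD for the app or 0.14 SD against it. With an unknown sign, neither a favourable nor an unfavourable result can be read plainly. The problem is more serious if final measurements are not taken on excluded participants, since those data may not be recoverable.

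A minor and separate point: initial data are collected at the onboarding meeting, within 48 hours of discharge, while the engagement rule applies at 24 hours. Someone onboarded between those times could be excluded before receiving the app.

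**What to change.** - Make the primary ROM analysis one of all enrolled app participants, whatever their engagement or readmission, using the final in-person measurement already planned. Where that measurement cannot be obtained, for example after readmission, report the number and the reason.
- Select controls on the same basis, as eligible patients who started home care, where records allow. Otherwise state the completer selection as a limitation.
- Keep the continuously engaged subset as a labelled sensitivity analysis.
- Keep low-engagement participants in the dose-response analysis, and report app-group readmissions.
- Reconcile the 24-hour and 48-hour passages.

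The cost is protocol wording, final measurements on those who would have been excluded (about 5 to 15 of 30 at 14 days under the assumptions above), and a search for control patients who started but did not complete. The protocol does not say whether such records exist. The app result may look less favourable. Both sides should change together: changing the app side alone would compare all app users with completers, a tilt of up to about 0.03 to 0.18 SD against the app under the same assumptions. None of this makes controls who had already completed care a randomised group.

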
45 to 64. Over the past decade, the smartphone has become an integral part of most people's lives. The latest Pew Research Data from February 2018 shows that 73% of individuals aged 50 to 64 own a smartphone (8). Smartphones would allow the patient to have direct multimedia access to a prescriptive exercise program designed by a licensed Physical Therapist without an in-person home visit, as well as to have communication directly with their Physical Therapist through secure in-app messaging or e-mail. The patient would benefit by having reduced intrusion in their home environment, convenient access to their Physical Therapist and their Physical Therapist's plan of care, and financial savings due to the elimination of home health care services following TKA. The Physical Therapist would benefit from the ability to quickly interact with the patient to mitigate any adverse events and to efficiently assist a greater number of patients compared to traditional home-based physical therapy. Third-party payors would benefit from drastically reduced home care costs for those recovering from TKA.

Objectives

The primary objective will be to determine the efficacy of the app for those recovering from TKA compared to traditional home care during the home bound portion of the patient's recovery from TKA by comparing ROM improvement outcomes between the intervention group and the control, as well as measuring the subjective improvement in functional outcomes for the intervention group by using the Short MAC. A secondary objective of the study is to determine the relationship between the intervention participants' self-reported frequency of engagement with the app and their qualitative and quantitative outcomes, otherwise known as the dose-response.

Methods

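### Total knee ROM improvement is the only outcome compared between groups, so an extension shortfall in the app group can be offset by extra flexion, or diluted by its variability, and be read as an equal outcome (minor)

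*Protocol*

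**What the plan says.** The Objectives set the between-group part of the primary objective as "comparing ROM improvement outcomes between the intervention group and the control". The Methods then name the variable: "objective outcomes will be assessed by measuring total knee ROM improvement". The analysis is one test: "A two-tailed t-test for two independent groups will be used to compare the means for total ROM improvement".

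No other outcome is compared between groups. The functional scale is restricted to one arm ("Subjective outcomes for the participants in the intervention group will be assessed by the Short MAC") and its role is descriptive ("Data from the Short MAC will be used to describe the overall subjective effect of the intervention").

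The reading of the result is also set in the Methods: "The primary hypothesis is that the intervention group will show a statistically equal outcome to the control group", which the protocol takes as showing that the app works as a cheaper substitute. No margin accompanies that statement. The Conclusion frames the aim broadly: "Use of smartphone technology has the potential to drive down costs while maintaining outcomes for this patient population".

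The protocol does not define total ROM. The words flexion and extension do not occur in it.

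**The concern.** An arc is a difference between two end-points. Two groups can have the same mean improvement in arc while differing at both ends, if one gains more flexion and the other more extension. A comparison of the total alone cannot show this.

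The direction of the error matters here. In a trial that seeks a difference, masking one costs power. This trial hopes to find no difference, so masking favours the hoped-for conclusion. The Short MAC cannot act as a check because controls do not have it. A statement that the app maintains outcomes would rest on one summed number per patient.

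That extension and flexion matter separately after knee arthroplasty is general clinical knowledge. The protocol does not discuss it.

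**Working it through.** **Inputs from the protocol (Methods).** About 30 patients per group; a two-tailed two-sample t-test; the variable is total knee ROM improvement; the last measurement is at the final in-person meeting of the homebound period. The protocol gives no figure on this point that could be reproduced.

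**Assumptions.** Total ROM is the extension-to-flexion arc. Alpha is 0.05 two-sided. SDs of improvement are 4 to 5 degrees for extension and 10 to 15 degrees for flexion. The two components are independent. All differences in degrees below are hypothetical.

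**Step 1: the identity.** Let F be maximum flexion and D the extension deficit, so arc = F − D. With 0 for start and 1 for end:

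improvement = (F1 − D1) − (F0 − D0) = (F1 − F0) + (D0 − D1) = flexion gain + extension gain.

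The group difference in mean improvement is therefore the sum of the two component differences. If the app group has −5 degrees in extension gain and +5 in flexion gain, the difference in the total is −5 + 5 = 0.

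**Step 2: invented example with two patients.** Both start at 10 to 70 degrees, arc 60.
- A ends at 10 to 100: (100 − 10) − 60 = 30.
- B ends at 0 to 90: (90 − 0) − 60 = 30.

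Both score 30, although A gained no extension (10 − 10 = 0) and B gained 10 (10 − 0).

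**Step 3: what the planned test would detect.** 10,000 trials were simulated per scenario, 30 per group, with the app group 5 degrees worse in extension gain. Entries are the share of trials with p < 0.05.

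| SD extension / flexion | Total, flexion +5 | Total, flexion +3 | Total, flexion 0 | Extension alone |
|---|---|---|---|---|
| 4 / 10 | 4.9% | 11.2% | 42.8% | 99.7% to 99.8% |
| 5 / 12 | 4.6% | 9.2% | 31.6% | 96.6% to 97.0% |
| 5 / 15 | 5.2% | 7.7% | 23.2% | 96.6% to 96.7% |

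Under full offset the test on the total rejects only at its false-positive rate. With no offset, the 5-degree difference passes fully into the mean of the total, but flexion adds its own variance: the SD of the total is √(4² + 10²) = 10.8, √(5² + 12²) = 13.0 and √(5² + 15²) = 15.8. Positive correlation between the components would widen these SDs and negative correlation would narrow them.

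**Step 4: the total on its own.** Power for a 5-degree difference by normal approximation is Φ(5 / (SD × √(2/30)) − 1.96). The smallest observed difference that reaches significance is 2.00 × SD × √(2/30).

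| Assumed SD of the total | Power at 5 degrees | Smallest significant difference (degrees) |
|---|---|---|
| 10 | 49% | 5.2 |
| 12 | 37% | 6.2 |
| 15 | 25% | 7.8 |
| 20 | 16% | 10.3 |

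**The case against.** The strongest objection is that component reporting is ordinary content for an SAP, and the protocol nowhere says that components will not be recorded or reported. That is fair as far as the extra analyses go. It does not reach the choice of variable used to "compare the means for total ROM improvement between the intervention group and the control group", or the reading of an equal result as success. Both are fixed in the protocol.

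Second, the arc definition is inferred. This stands. It is the ordinary meaning and no other is offered, but the fix should begin with a definition.

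Third, full cancellation needs the app to be worse in one component and better in the other, and nothing in the documents suggests that it would be. This also stands. A difference in one component alone is diluted, not hidden. A reader might infer that a masked deficit is to be expected, or that app patients would be left with a lasting contracture. The documents support neither: they give no component data, and measurement ends with the homebound period.

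Fourth, the larger weakness is that non-significance is read as equality without a margin. The no-offset column agrees: the total misses a 5-degree extension shortfall in most simulated trials without any cancellation. So a rule that neither component be worse, judged by significance, would repeat the fault. The remedy has to use intervals and a margin.

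Finally, how many control records hold both end-points is unknown, so the cost of the component comparisons cannot be called negligible.

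**Conclusion.** The point holds as a minor one. Total ROM improvement is the only between-group variable. On its ordinary meaning, an extension shortfall at the final homebound visit can be offset by flexion or diluted by flexion variability, and the result read as equal.

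The offset is exact arithmetic. Its consequence for the test is an illustration: for a 5-degree extension shortfall, about 5% of trials significant on the total with full offset, 8% to 11% with a 3-degree offset and 23% to 43% with none, against 97% to 99.8% on extension alone. These figures rest on 30 per group, alpha 0.05, independent components and the assumed SDs. How likely such a shortfall is cannot be determined from the documents.

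**What to change.** - Define total ROM as the arc from maximum extension to maximum flexion, and keep its improvement as the headline measure.
- Record maximum extension and maximum flexion separately in the app group, and extract both from control records where they are documented.
- Prespecify, as supportive analyses, the between-group difference in improvement for each component with a 95% CI.
- Limit any statement that the app maintains ROM to what these intervals support against a margin that the sponsor justifies. A non-significant test should not be enough.
- Keep control records that give only an arc in the total-ROM analysis, and report how many lack the components.

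**Cost.** No new measurement in the app group, since an arc already requires both end-points, and two more lines of analysis. The component comparisons may rest on fewer than the roughly 30 controls, and the claim of maintained ROM becomes slightly harder to reach. The extraction rule should be set before control data are taken from records.

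### App dose is defined only as self-reported frequency, with no recall period, collection time or other source, and no evidence source is named for the 24-hour engagement exclusions

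*Protocol*

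**What the plan says.** The dose measure is stated three times, each time the same way.

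- Objectives, with outcomes on the other side of the relationship: "A secondary objective of the study is to determine the relationship between the intervention participants' self-reported frequency of engagement with the app".
- Methods, outcome paragraph: "The intervention participants' self-reported frequency of app usage will be compared to the participants' outcomes to determine the dose-response of the app".
- Methods, analysis: "The relationship between the Participants self-reported frequency of app usage and their combined subjective and objective outcomes will be used to understand the dose-response".

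None of these places says when the report is taken, over what period participants look back, or whether any other usage record exists. The intended use is ambitious: "Information about dose-response will be integral in establishing guidelines regarding frequency of app usage for optimal results".

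Engagement also decides whose data are kept. Intervention data are excluded "if they do not engage with the app within 24 hours of discharge from the hospital", or "if the participant neglects to engage with the app over any 24-hour period during the study". The protocol does not say what evidence is used to apply either rule.

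Two further statements in the Methods bear on the point. Participants are encouraged to use the app three to five times a day, to the extent they can. There are also scheduled contacts, made for safety: "a physical therapist will contact the intervention group participant via phone or e-mail every 24 to 48 hours to ensure no adverse events have occurred". Recording app use at that contact is not mentioned. The intervention group is to have about 30 participants.

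**The concern.** A guideline on frequency needs a dose measured well enough to rank people by how much they used the app. Self-report over an unstated period is a weak basis for that, for three reasons.

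1. Ordinary recall error adds noise to the dose and weakens any association.
2. An encouraged range of three to five a day gives participants a figure to report toward, which narrows the spread of reported doses.
3. Participants who feel they are doing well may report more use, which would create or strengthen an association.

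The first mechanism weakens the relationship. The other two can distort it in either direction. With about 30 people there is little precision to spare.

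The silence about the 24-hour exclusions is a related gap. Those rules settle who enters the range-of-motion comparison, so the source of engagement data reaches the primary analysis through who is excluded.

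This cannot be left to a statistical analysis plan. A plan can choose a model, but it cannot recover usage data that were never collected.

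**Working it through.** The protocol gives no figure for dose variability, reporting error or power, so there is nothing to reproduce. What follows is illustration.

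**Inputs.** From the Methods: n about 30 and an encouraged three to five sessions a day. Assumed: true between-person SD 0.8 sessions a day, random error SD e from 0.5 to 1.0, two-sided alpha 5%, power 80%.

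**Random error and the slope.** Reliability = 0.8² / (0.8² + e²).

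- e = 0.5: 0.64 / (0.64 + 0.25) = 0.72, so the slope is attenuated by 28%.
- e = 1.0: 0.64 / (0.64 + 1.00) = 0.39, so the slope is attenuated by 61%.

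**Random error and power.** By Fisher's z, the smallest correlation detectable at n = 30 is tanh[(1.960 + 0.842) / √27] = tanh(0.539) = 0.49. The true correlation must then be 0.49 / √reliability:

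- reliability 0.7: 0.49 / 0.837 = 0.59
- reliability 0.4: 0.49 / 0.632 = 0.78

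For a true correlation of 0.5, the observed correlation is 0.5 × √reliability and power is about Φ(atanh(r) × √27 − 1.96):

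| Reliability | Observed r | Power |
|---|---|---|
| 1.0 | 0.50 | 81% |
| 0.8 | 0.45 | 71% |
| 0.6 | 0.39 | 57% |
| 0.4 | 0.32 | 40% |

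**Reporting toward the target.** Suppose reported = 4 + 0.5 × (true − 4), with no random error. Reported doses have half the spread, so the slope on reported use is twice the true slope while the correlation is unchanged. Now add random error with SD e. The slope is multiplied by (0.5 × 0.64) / (0.25 × 0.64 + e²) = 0.32 / (0.16 + e²).

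- e = 0: 0.32 / 0.16 = 2.0
- e = 0.4: 0.32 / 0.32 = 1.0
- e = 0.5: 0.32 / 0.41 = 0.78

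Under this compression the slope may be inflated, unchanged or attenuated, depending on an error size the protocol does not give.

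**What the planned contacts can resolve.** A contact at most 48 hours after the last one shortens recall but does not by itself show a 24-hour gap. Daily counts need not show one either: a session at 08:00 on one day and the next at 20:00 on the following day leaves 16 + 20 = 36 hours without use, although each day has one session. Time stamps would show it.

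**Sensitivity of the retained set.** Take an assumed 14-day homebound period and an assumed daily chance of a missed day of 1%, 2% or 5%. If every lapse is found, the number retained is 30 × 0.99¹⁴ = 26, 30 × 0.98¹⁴ = 23 or 30 × 0.95¹⁴ = 15. If none is found it is 30. How a lapse is detected therefore matters.

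**The case against.** The best defence is that the protocol is open and consistent. It defines the secondary objective as a relationship with self-reported frequency, in three places that agree. Nothing is concealed or contradictory, and that stands.

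A reader might also infer more than the text supports:

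- *The 24-hour rule cannot be verified, or rests on recall.* Self-report is attached only to the dose-response frequency. For the exclusions the protocol is silent, so the supportable statement is that no source is specified.
- *The contacts ask only about adverse events.* The protocol gives safety as their purpose, not their full content. Usage reports might already be taken there.
- *Participants shade their reports to avoid exclusion.* The protocol does not say they are told of the rule.
- *Self-report must flatten the slope.* That follows for random error unrelated to true use or outcome. It does not follow for reporting toward a target, so the 28% to 61% is not a net estimate.
- *A question at the contact cures the problem.* It is still self-report, and the pull toward the target remains.

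Two other objections stand in part. Asking about use every 24 to 48 hours prompts only the app group, because the controls have already completed their care, so it could touch the primary comparison. And since participants use the app as far as they are able, those recovering better may use it more. A better count does not remove that confounding.

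**Conclusion.** The point holds as a limited one. App dose is fixed as self-reported frequency with no recall period, collection time or other source, and the engagement exclusions have no named source of evidence, while the dose-response is expected to inform usage guidelines.

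The size depends on assumptions that the protocol does not anchor. Purely random error would take 28% to 61% off the slope under the SDs assumed above. At reliability 0.7 to 0.4 it would raise the true correlation needed for 80% power at n = 30 from 0.49 to between 0.59 and 0.78. The 0.49 reflects the sample size alone, and no better measure lowers it. With the other reporting mechanisms included, the direction of the net bias is not established.

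The direct effect is on a secondary objective. The primary comparison is affected only through who is excluded. This is a worthwhile, low-cost improvement, not a flaw that invalidates the trial.

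**What to change.** 1. **Dose.** Define it as mean sessions per day from time-stamped app records, if the app keeps them (the protocol does not say).
2. **Fallback.** If it does not, record at each contact already planned the dated number of sessions in each 24-hour window since the last contact. State plainly that this is still self-report, with recall of up to about 48 hours.
3. **Exclusions.** Name the same source wherever the protocol relies on engagement, and say how a 24-hour period is counted, since window counts can miss a gap that time stamps would show.
4. **Interpretation.** Describe the dose-response as an exploratory association, and soften the statement that it will underpin frequency guidelines.

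**Cost.** A data export, or one added question at an existing contact, with no added staff or visits. The downside of the question is that asking may prompt use in the app group; an export avoids this. The change should be made before data collection starts, because usage not recorded at the time cannot be rebuilt reliably.
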